## C. PRELIMINARY WORK

**C.1. Our interdisciplinary scientific team (see key personnel):** Under the leadership of Drs. [name], [name], and [name], we have assembled an impressive cadre of senior and junior scientists with expertise in ADRD screening and diagnosis (Drs. [name], [name], and [name]); Machine Learning ([name] and [name]); Psychometrics (Drs. [name], [name], and [name]); Medical informatics (Drs. [name], [name], and [name]); and Implementation Science ([name], [name], and [name]). The members of this team have a track record of collaborating in conducting research activities similar to the proposed activities within this application including creation and validation of PROs and utilization of ML algorithms to improve ADRD detection through the EHR. In the following section, we summarize the results of preliminary and relevant studies conducted by members of this team which informed the design of our proposed studies. Such preliminary studies are selected from a large repository of research conducted by this team (see scientific contributions within the key personnel).

**C.2. The limited impact of the current AWV on early detection of ADRD:** We conducted a retrospective matched cohort study to examine the impact of the AWV on the detection of ADRD. The cohort included 5% sample of Medicare beneficiaries continuously enrolled for 12 months before and after an index ambulatory visit with no evidence of ADRD before the index date. The matching process resulted in 66,399 matched pairs of beneficiaries with and without an AWV. Outcomes included 12 months post-index visit claims-based measurements of new ADRD diagnoses, medications for ADRD, and cognitive care-related diagnostic work up such as neuropsychological testing, brain imaging, blood tests for thyroid-stimulating hormone (TSH), serum B12, folate, or syphilis. *There were no clinically relevant differences between the AWV and control groups in the rates of incident ADRD diagnoses (6.16% versus 6.86%, p<0.001) and the initiation of ADRD medications (1.00% versus 1.08%, p=0.148).* While the AWV was correlated with an increase in some measures of cognitive care (e.g., TSH, B12, and folate testing), we did not find that the current AWV increased recognition of undetected ADRD. Enhancing the AWV with data from the PDM, the QDRS, or both may overcome current AWV shortcomings.

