#### **D.7.b. Incidence of ADRD for the pragmatic cluster-randomized comparative effectiveness clinical trials:**

For the two pragmatic trials and using similar approach from previous studies, we will use data captured by the EHR to assess for two outcomes. The primary outcome measure will be any new ADRD case identified (documented in the EHR) within 12 months of the Annual Wellness Visit (index visit). The secondary outcome measures will be any services related to cognitive diagnostic assessment in the post Annual Wellness Visit (index) period that providers may order to diagnose or exclude ADRD. Specifically, the metrics

of diagnostic assessment will be evaluated as proportions of patients with a record of 1 or more of:

- Laboratory tests for TSH, serum B12, folate, or syphilis; individually or combined at any point during the 90 days after index
- Neuropsychological testing, including testing by psychologist or physician, technician administrator, computer, or other providers during the 12 months after index date
- Brain imaging testing (computed tomography, magnetic resonance imaging, positron emission tomography, magnetic resonance angiogram) of the head and neck, brain, or skull during the 12 months after index date
- Medications approved for management of ADRD (cholinesterase inhibitors, memantine) during the 12 months after index date

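### In D.7.b the laboratory and imaging metrics count tests done for any reason and ignore the patient's earlier testing, which dilutes arm differences by an unknown amount; pre-index adjustment is the cheap remedy.

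*Combined protocol and SAP*

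**What the plan says.** D.7.b describes the secondary outcome by its purpose: "any services related to cognitive diagnostic assessment in the post Annual Wellness Visit (index) period that providers may order to diagnose or exclude ADRD". It then gives a counting rule, under which the metrics "of diagnostic assessment will be evaluated as proportions of patients with a record of 1 or more of" four listed items:

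- **Laboratory:** "Laboratory tests for TSH, serum B12, folate, or syphilis; individually or combined at any point during the 90 days after index".
- **Neuropsychological testing:** "Neuropsychological testing, including testing by psychologist or physician, technician administrator, computer, or other providers during the 12 months after index date".
- **Imaging:** "Brain imaging testing (computed tomography, magnetic resonance imaging, positron emission tomography, magnetic resonance angiogram) of the head and neck, brain, or skull", within 12 months of the index date.
- **Medication:** "Medications approved for management of ADRD (cholinesterase inhibitors, memantine) during the 12 months after index date".

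No item requires a recorded indication, a positive screen or a referral. None looks back before the index visit, and the drug item does not ask for a new start. D.8.b sets out nonlinear mixed models with clinic random effects for incidence and for acceptance of work-up. It adds no condition to the D.7.b metrics and no patient-level covariate.

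Section C.2, on the team's earlier claims study, says: "While the AWV was correlated with an increase in some measures of cognitive care (e.g., TSH, B12, and folate testing"), and reports that recognition of undetected ADRD did not rise.

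**The concern.** The stated purpose is narrower than the counting rule. Thyroid, B12 and folate tests and head or neck scans are also ordered for reasons unrelated to cognition. Under the rule as written, a routine TSH at day 60 in a patient on thyroid replacement counts as cognitive work-up. So does a head CT after a fall.

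Two consequences follow for the laboratory and imaging metrics. Background testing that is equal across arms pulls the arm difference toward zero. And because each arm has only 5 practices, ordinary differences in how practices order tests add noise that has nothing to do with screening for ADRD. What is at stake is how sensitive and how interpretable two of the four secondary process metrics will be.

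**Working it through.** **Inputs from D.8.c.** Two-sided alpha 0.05; ICC 0.01; conservative layout of 5 practices per arm, M = 173.2 patients per practice, 866 per arm; historical layout of M = 240, 1,200 per arm.

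**Formula.** Inflation factor IF = 1 + (M − 1) × ICC. SE = √[(p₁q₁ + p₂q₂) × IF / n], where q = 1 − p. Power = Φ(|p₂ − p₁| / SE − 1.96).

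**Step 1: the plan's own figures for 6% v 13%.**

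- Conservative: IF = 1 + 172.2 × 0.01 = 2.722; SE = √[(0.0564 + 0.1131) × 2.722 / 866] = 0.0231; power 85.8% (stated 86%).
- Historical: IF = 1 + 239 × 0.01 = 3.39; SE = 0.0219; power 89.2% (stated 89%).

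The formula reproduces the plan. D.8.c gives no power for the D.7.b metrics.

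**Step 2: dilution model (assumption).** Let s be the proportion with cognition-driven work-up and b the proportion tested for other reasons, with the two independent and b equal in all arms. The observed proportion is p = b + (1 − b)s. The arm difference is therefore (1 − b)(s₂ − s₁).

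**Step 3: one case in full.** Take s = 10% v 20% and b = 30%.

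- p₁ = 0.30 + 0.70 × 0.10 = 0.37; p₂ = 0.30 + 0.70 × 0.20 = 0.44.
- SE = √[(0.2331 + 0.2464) × 2.722 / 866] = 0.0388.
- Power = Φ(0.07 / 0.0388 − 1.96) = 44%.

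At b = 0 the SE is 0.0280 and power is 95%. The difference shrinks and the binomial variance grows as well.

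**Step 4: the range, conservative layout.** Neither s nor b for these metrics is in the documents, so three pairs of s are shown. The last two borrow the plan's incidence and acceptance rates purely as illustrations of rare and common work-up.

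| True work-up | b = 0 | 10% | 20% | 30% | 50% | 60% | 70% |
|---|---|---|---|---|---|---|---|
| 10% v 20% | 95% | 77% | 58% | 44% | 25% | 19% | 14% |
| 6% v 13% | 86% | 54% | 35% | 25% | 14% | 11% | 9% |
| 44% v 66% | >99% | >99% | >99% | 99% | 92% | 83% | 69% |

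**Step 5: ordering habits.** At the plan's ICC and an observed rate of 37%, the between-practice SD is √(0.37 × 0.63 × 0.01) = 4.8 points. Its contribution to the SD of a difference between two arms of 5 practices is √(2/5) × 4.8 = 3.1 points, against the diluted difference of 7 points in Step 3. This is already inside the SE above, so it is noise rather than bias. It is the part that a patient-level record of earlier testing could reduce.

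**The case against.** Several points on the other side carry weight.

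**All-reason counting is valid under randomisation.** Background testing is balanced in expectation, and the clinic random effects allow for practice variation. What is estimated is an effect on service use, attenuated if background is equal. This stands. The problem is loss of sensitivity and precision, not bias.

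**The size is unknown.** This also stands. If work-up were as common as 44% v 66%, dilution would cost little. Those figures, however, are acceptance rates after a positive screen, whereas the D.7.b metrics are proportions of patients with no such restriction. Rates over all patients could well be lower, which is where dilution costs most.

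**The earlier study does not prove the point.** C.2 compared patients with and without an AWV and was not randomised. Here every arm has the AWV, and extra tests without extra diagnoses also fit testing to exclude ADRD, which D.7.b expressly includes. C.2 is consistent with non-specific laboratory testing; it neither establishes it nor supplies b.

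**Not all four items are affected.** Neuropsychological testing is directed at cognition. A reader might infer that the drug item is equally unspecific, but it is confined to drugs approved for ADRD, and C.2 reports initiation of only 1.00% and 1.08%. Its issue is one of label: a prescription is treatment, and C.2 itself lists medications apart from diagnostic work-up.

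**The items may already be separate.** D.7.b speaks of metrics and proportions in the plural, with different windows, so four separate proportions is a natural reading. A single composite is also possible and would be the most exposed, because unrelated laboratory testing would feed straight into it. The text should settle this.

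**Restricting to orders with a cognitive reason could introduce bias.** Under D.6 the decision support shows clinicians recommendations on diagnostic work-up, so orders in the screening arms may be more likely to carry a cognitive reason. That would exchange attenuation for ascertainment that differs by arm. This objection stands and shapes the fix.

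**Conclusion.** The point holds for the laboratory and imaging metrics. They count tests whatever the reason and take no account of earlier testing, so unrelated testing at an equal rate b scales the arm difference by (1 − b). At assumed true work-up of 10% v 20%, power falls from 95% to 77% at b = 10% and 44% at b = 30%; at 44% v 66% it stays above 80% to about b = 60%. These figures rest on assumed values of s and b, on independence and equal background across arms, and on the plan's ICC of 0.01.

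A reader might go further and infer that the definition hides the effect of screening, or that it undermines Aim 2. The documents do not support either. The primary outcome, a new documented ADRD diagnosis, does not use these records. The powered secondary hypothesis concerns acceptance of recommended work-up, and nothing says that acceptance is derived from the D.7.b items. D.4 also plans screening, referral and acceptance rates beside them. This is a worthwhile improvement to secondary process metrics, not a threat to the main result.

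**What to change.** In D.7.b, with a matching sentence in D.8.b:

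1. State the model for these metrics (presumably the same mixed model with clinic random effects). For each laboratory and imaging metric, include as a covariate whether the same patient had that test in the same-length window before the index AWV: 90 days for laboratory tests, 12 months for imaging. Take it from the same Epic extraction.
2. Report the four items as separate proportions, and label ADRD medication as treatment rather than diagnostic assessment.
3. Keep the all-reason count as the main version of each metric. A count of cognition-linked orders may be shown as a sensitivity analysis only, because decision support in the screening arms may change how orders are coded.

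The cost is SAP wording and extra look-back fields in an extraction that is already planned. The adjustment recovers precision to the extent that earlier testing predicts later testing; it does not restore the b = 0 figures. One detail needs care. D.4 describes the tools as active at other primary care visits as well as the AWV, so the extraction should flag any look-back time that falls after a patient's first exposure to them, since testing in that time is not a true baseline.

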#### D.8. Analysis Plan

**D.8.a. Primary Aim 1:** *Evaluate the predictive performance of the PDM, the QDRS, and the combined approach in the early detection of ADRD, compared to the gold standard diagnoses.*

For Primary Hypothesis 1, the screening approaches will be validated by evaluating the Area Under the Curve (AUC) for the PDM, the QDRS, and the combined approach. For the purpose of Aim 1, the PDM and the QDRS will be administered in the same sample of patients to increase power while retaining internal validity of conclusions. The AUC will be calculated from the plot of the sensitivity (y-axis) by 1 – specificity (x-axis) across all possible discrete screening score values. For the combined approach, screening will be considered positive if either PDM or QDRS are positive. The gold standard diagnosis will be determined as described in **D.7.a**. We hypothesize that the AUC, as well as the overall % accuracy of classifications, will be 0.85 or greater for the combined method, and 0.75 or greater for PDM and the QDRS.

For Secondary Hypothesis 2, dependent AUCs will be compared using the method that extends DeLong et al.'s nonparametric method to be valid for clustered data by using the Rao and Scott concepts for clustered binary data. The AUCs of different methods are dependent in the Aim 1 study because they are calculated on the same sample of patients. We hypothesize that the combined approach of PDM and QDRS will have statistically better AUC than PDM or the QDRS alone. In addition, the screening approaches will be compared on the overall % accuracy of classification (i.e., a simple proportion based on 0/1 data for each person) using nonlinear mixed models to account for correlated outcomes due to dependent methods and practice-clustered data.

Potential problems & alternative strategies: The distributional assumptions for the binary outcomes are minimal, which will decrease the need to consider alternative analytic methods and models. However, to ensure the analytic methods appropriately account for the clustering effect when estimating standard errors and p-values, we will perform bootstrap estimation (i.e., using 1,000 datasets resampled with replacement at the person level) of the standard errors and confidence intervals surrounding the estimated values for AUC and % accuracy, and the estimated values for the difference in these values between screening approaches. In addition, if missing data occur, we will impute data using the simulation-based “Multiple Imputation” method, in which multiple complete datasets with plausible values for missing data are generated using model-based prediction, and analytic results from imputed datasets are aggregated to calculate appropriate standard errors and p-values in the presence of imputed data. We will use 100 imputed datasets, even though 10 to 50 are considered sufficient. Inclusion of potential auxiliary variables in the imputation model will be considered. A sensitivity analysis will be performed using participants with complete data.

**D.8.b. Primary Aim 2:** Evaluate the practical utility and effect of the PDM, and the combined methods in improving the annual rate of new documented ADRD diagnosis in primary care practices.

For Primary Hypothesis 1, three pragmatic screening approaches (AWV alone, AWV + PDM, and AWV + PDM + QDRS) will be compared on the annual incidence rate of EHR documented ADRD using nonlinear mixed models to account for clinic-clustered data. In the two pragmatic trials, different patients are randomized (via their clinics) to each of the 3 arms, making the outcomes independent between the three screening approaches; however, data will still be correlated for Aim 2 due to clustering of patients within clinics, which will be handled by random effects in the mixed models. We hypothesize the incidence rate will be 6% using AWV alone and 13% with the screening approach that combines AWV + PDM + QDRS. Incidence rates for all arms, including for AWV + PDM, will be calculated along with their 95% confidence interval.

For Secondary Hypothesis 2, the analyses will be the same as described for Hypothesis 1 of Aim 2, except that the outcome will be acceptance rates for recommended ADRD diagnostic work-up following positive screen. We hypothesize the acceptance rate will be 44% using AWV alone and 66% with the screening approach that combines AWV + PDM + QDRS.

Potential problems & alternative strategies: Same as those described for Aim 1 above.

**D.8.c. Sample Size & Power:** Calculations were performed with PASS, a comprehensive power and sample size software. All calculations assume two-sided tests and alpha = 0.05. For study 1 (i.e., Aim 1), a sample size of 15 cluster pairs consisting of 400 persons (26.667 persons per cluster) will provide 81% power to compare population values of 75% versus 85% in the outcome of % accuracy of classification. This is based on using nonlinear mixed models to compare two paired (i.e., dependent) proportions. The proportions are considered dependent instead of independent because all three screening approaches for study 1 will be performed in the same sample of 400. This approach was selected because it will increase power by allowing participants to serve as their own controls. Moreover, it is appropriate for a diagnostic validity study to compare methods in the same sample (i.e., method contamination is not an issue). This calculation assumes that participants are recruited from 15 clinics (i.e., clusters) and that the within-pair coefficient of variation (CV) between clusters is .058. The CV was calculated as  $CV = \text{SQRT} (ICC \times (1 - \phi) / \phi)$ , where the intraclass correlation coefficient (ICC) was assumed to be 0.01, and phi is 0.75 (i.e. the proportion of accuracy for one of the standard screening methods). The power will be slightly greater than 81% to detect values of 75% versus 85% in the AUC, based on power for comparing two dependent AUC's, assuming discrete cutoff values, and accounting for a sample inflation factor (IF), where  $IF = [1 + (M - 1) * ICC]$ , M = average number of persons per cluster, and the ICC is 0.01.

Because the other studies are two separate pragmatic clinical trials, participants will be cluster-randomized to three different arms. This approach ensures that rigorous testing of the outcomes (incident ADRD detection and acceptance of subsequent diagnostic assessments) is not contaminated by the other screening approaches in other arms of interest. In addition, the 400 patients in study 1 will be excluded from the two pragmatic trials to avoid contamination. The total sample for each pragmatic trial will be slightly over 2,600, if each of enrolled practice screen conservatively 175 patients per year for a total of two years of screening. Alternatively, the total sample size for each trial will be 3,600, if we recruit, as we have in past trials, 200 patients per clinic. The table below shows the power for comparing ADRD incidence and acceptance rates between two different arms under the conservative and historical recruitment scenarios. Calculations were based on using nonlinear mixed models to compare two independent proportions, assuming cluster randomization (i.e., level-2 randomization) and the

ICC is 0.01. The “AWV alone” arm is expected to have ADRD incidence of 6% and acceptance rate of 44%. The table shows that power will exceed 80% to detect ADRD incidence of 6% vs 13%, even under conservative recruitment projections, and power for comparing acceptance rates will be 99%.

Outcome	Conservative recruitment* (N = 2,600)	Projected (feasible historically) recruitment* (N = 3,600)
ADRD incidence 6% vs 13%	86%	89%
Acceptance 44% vs 66%	99%	99%

\*Conservative recruitment = Total of 2,600 patients with 866 patients and 5 clusters per each of 3 arms; power for pairwise comparisons based on 1,732 patients with 866 patients and 5 clusters per each of 2 arms, and M = 173.2 patients per cluster. Historical recruitment = Total of 3,600 patients with 1,200 patients and 5 clusters per each of 3 arms; power for pairwise comparisons based on 2,400 patients with 1,200 patients and 5 clusters per each of 2 arms, and M = 240 patients per cluster.

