In response to the RFA-AG-20-051 call for the "validation, and translation of screening and assessment tools for measuring cognitive decline," our interdisciplinary scientific team is proposing to execute a clinical validation study, one pragmatic trial and one additional replicated pragmatic trial among patients from diverse rural, suburban and urban primary care practices in two independent sites located in central Indiana and south Florida. As required by the RFA, the first study will be a single-arm clinical validation (NIH Stage III) study of our developed early ADRD detection approaches; Passive Digital Marker (PDM) and the Patient Reported Outcome (PRO) tool, the Quick Dementia Rating System (QDRS) for discriminating gold standard ADRD diagnoses for a sample of 400 older primary care patients served in the two states. The other studies will be two pragmatic cluster-randomized controlled comparative effectiveness (NIH Stage IV) trials to incorporate the PDM and the QDRS within the Medicare paid Annual Wellness Visit (AWV) for a cohort of patients from practices across the two independent sites, with practices randomized in each pragmatic trial to one of the 3 arms (the AWV alone, the AWV with PDM, and the AWV with both the PDM and the QDRS).

These studies will support the following aims:

**Primary Aim 1:** Evaluate the predictive performance of the PDM, the QDRS, and the combined (PDM + QDRS) approach in the early detection of ADRD, compared to the gold standard diagnoses.

*Primary Hypothesis 1:* The Area Under the Curve (AUC) for the combined approach (PDM + QRDS) will be 0.85 or greater and the AUC for the PDM or the QDRS will be 0.75 or greater.

*Secondary Hypothesis 2:* The combined approach (PDM + QDRS) will have statistically better AUC than each individual approach alone.

**Primary Aim 2:** Evaluate the practical utility and effect of the PDM, the QDRS, and the combined approach (PDM + QDRS) in improving the annual rate of new documented ADRD diagnosis in primary care practices.

*Primary Hypothesis 1:* In comparison to the AWV alone, the combined approach (PDM + QDRS) within the AWV will increase the incidence rate of ADRD over the subsequent 12 months from 6% to 13%.

*Secondary Hypothesis 2:* In comparison to the AWV alone, the combined approach (PDM + QDRS) within the AWV will have higher acceptance rates for recommended ADRD diagnostic work-up following a positive screen from 44% to 66%.

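### Overall % accuracy, an Aim 1 target and the basis of its sample size, mostly reflects specificity if ADRD is uncommon and works against the either-positive combined rule

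*Combined protocol and SAP*

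**What the plan says.** Under Primary Hypothesis 1, D.8.a of the combined protocol and SAP states: "We hypothesize that the AUC, as well as the overall % accuracy of classifications, will be 0.85 or greater for the combined method". Each tool on its own is given a threshold of 0.75 on the same two measures. For the comparison of methods it adds: "In addition, the screening approaches will be compared on the overall % accuracy of classification", where accuracy is "a simple proportion based on 0/1 data for each person". The combined rule is: "For the combined approach, screening will be considered positive if either PDM or QDRS are positive".

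D.8.c bases the Aim 1 sample (400 persons, 15 clinics, 81% power) on "75% versus 85% in the outcome of % accuracy of classification". It says AUC power would be slightly higher, but gives no case count and no correlation between the two AUCs. D.9 offers a rise from 75% to 85% in AUC or in accuracy as alternative forms of the same expected gain.

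The Specific Aims state both Aim 1 hypotheses on AUC alone, the first being "The Area Under the Curve (AUC) for the combined approach (PDM + QRDS) will be 0.85 or greater".

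The plan gives no expected ADRD prevalence for the 400. It does not say whether MCI, one of the four consensus categories in D.7.a, counts as positive. D.8.a sets no target for sensitivity or specificity.

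**The concern.** Accuracy weights sensitivity by the share of participants with ADRD and specificity by the rest. If that share is small, a tool can miss most cases and still score well, while a sensitive screen is penalised for its false positives. For an early-detection tool, missed cases are the failure that matters most.

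The combined approach is affected most directly. It is built to find more cases at the price of more false positives, and raw accuracy at low prevalence charges heavily for the second and credits little for the first. Two things are at stake: a secondary comparison that could rank the combined approach below its own components while it detects more ADRD, and a sample size resting on an accuracy gain that the rule may be unable to produce.

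**Working it through.** **Inputs.** Targets 0.85 and 0.75 and the either-positive rule (D.8.a). 400 persons, 15 clusters, 26.667 per cluster, ICC 0.01, 75% versus 85% (D.8.c). PDM one-year combined-model sensitivity 76.01% (Table 3; the specificity column is lost in the available text, so this follows the order of the headings). Prevalence p is **assumed**: 6% and 13% are Aim 2 rates of 12-month documented incidence, used only for want of an Aim 1 figure. Higher values are shown too.

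**1. The plan's power.** CV = √(0.01 × 0.25/0.75) = 0.0577. For matched cluster pairs:

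power = Φ(√[(k − 2)(p1 − p2)² / V] − 1.96), with V = p1q1/m + p2q2/m + CV²(p1² + p2²).

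V = 0.00703 + 0.00478 + 0.00428 = 0.01610, and √(13 × 0.01/0.01610) = 2.842. Power = Φ(0.882) = 81.1%, matching the stated 81%. Prevalence does not enter this formula.

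**2. Flagging nobody.** Accuracy = p × sensitivity + (1 − p) × specificity. With sensitivity 0 and specificity 1 this is 1 − p.

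| p | ADRD cases in 400 | accuracy |
|---|---|---|
| 6% | 24 | 94% |
| 13% | 52 | 87% |
| 15% | 60 | 85% |
| 20% | 80 | 80% |
| 25% | 100 | 75% |
| 30% | 120 | 70% |

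The empty rule meets 85% up to p = 15% and 75% up to p = 25%. Its AUC is 0.50.

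**3. Ranking (illustrative tools, p = 13%).**
- Sensitivity 90%, specificity 75%: 0.13 × 0.90 + 0.87 × 0.75 = 77.0%.
- Sensitivity 20%, specificity 95%: 0.13 × 0.20 + 0.87 × 0.95 = 85.3%.

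Accuracy prefers the tool that misses four cases in five.

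**4. Ceiling for the combined rule.** At fixed cut-offs, everyone positive on one tool is positive on the combination, so combined specificity cannot exceed either tool's. Combined sensitivity is at most 1. Hence the gain over a tool with sensitivity s is

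p(Se_comb − s) + (1 − p)(Sp_comb − Sp_tool) ≤ p(1 − s).

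- p = 6%: at most 6 points, whatever s is.
- p = 13%, s = 0.76: 0.13 × 0.24 = 3.1 points.
- A 10-point gain with s = 0.76 needs p ≥ 0.10/0.24 = 42%.
- A 10-point gain needs s ≤ 1 − 0.10/p: 23% at p = 13%, 50% at 20%, 67% at 30%.

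**5. Reversal (illustrative).** Take two conditionally independent tools, each with sensitivity and specificity 75%, at p = 13%. Combined sensitivity = 1 − 0.25² = 93.75%; specificity = 0.75² = 56.25%. Accuracy falls from 75% to 0.13 × 0.9375 + 0.87 × 0.5625 = 61.1%, while detection rises from 75% to about 94%.

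**6. Power on AUC.** With Hanley–McNeil variances, the plan's inflation factor 1 + 25.667 × 0.01 = 1.257, and an assumed correlation of 0 to 0.7 between the two AUC estimates, power for 0.75 versus 0.85 is about 21% to 55% at p = 6% and 39% to 85% at p = 13%.

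**The case against.** The strongest reply is that accuracy does not decide Aim 1. Both hypotheses in the Specific Aims rest on AUC, Secondary Hypothesis 2 is tested by a clustered comparison of AUCs, and accuracy is an addition. This stands. A reader might infer that Aim 1 could be declared a success by a tool that detects no one. The documents do not support that: the 0.85 statement in D.8.a covers AUC and accuracy together, and the empty rule's AUC is 0.50.

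A reader might also take 87% to 94% as following from the plan's own ADRD rates. It does not. The 6% and 13% are documented incidence in Aim 2, whereas Aim 1 uses a consensus diagnosis. The plan says that half of people with ADRD are never diagnosed, so the gold-standard share could be higher, and higher again if MCI counts as positive. Against that, Table 6 removes people with a coded ADRD or MCI diagnosis or a prescription for dementia medication. Above 15% the empty rule misses 85%.

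The margins at 13% are thin as well. The 20%/95% tool passes by 0.25 points and at 14% scores 84.5%. The empty rule's approximate 95% lower bound, with the plan's inflation factor, is 83.3%.

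Finally, a PDM with about 76% sensitivity is nothing like an empty rule. That is fair, and it is why the realistic risk is a combined rule marked down rather than an empty rule passed. None of these replies removes the ceiling in step 4.

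**Conclusion.** The concern holds for the accuracy targets, the accuracy comparison and the power calculation based on accuracy. It does not reach the AUC hypotheses, which remain primary.

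That accuracy mostly reflects specificity when ADRD is uncommon is arithmetic. How far this matters depends on a prevalence the plan does not state. The ceiling on the combined rule needs only fixed cut-offs. It puts the 10-point gain out of reach at 6%, and at 13% out of reach unless the single tool detects 23% of cases or fewer. Over a tool with 76% sensitivity the gain needs about 42% prevalence. The 76% comes from development data rather than the Aim 1 gold standard, so it is indicative.

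The 81% is correctly computed for its inputs, and 400 has not been shown to be too few for the AUC comparison: at 13% prevalence and a correlation of 0.7, AUC power is about 85%. The statement that AUC power slightly exceeds 81% cannot be checked without a prevalence and a correlation.

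**What to change.** **D.8.a.** Keep AUC as the primary measure. Replace the accuracy targets and the accuracy comparison with sensitivity among gold-standard ADRD and specificity among the rest, each compared between methods by the same clustered paired approach. If accuracy is reported at all, make it descriptive and print 1 − prevalence beside it.

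**D.8.c.** State the positive class (including where MCI falls) and the expected prevalence. Restate power on AUC at the expected case count, with the assumed correlation, in place of the accuracy-based 81%. Give the planned precision for sensitivity.

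**Cost.** No new data are needed, but this is more than rewording because Aim 1 needs a new power calculation, which may be less favourable. Sensitivity will rest on few cases. Its 95% half-width, 1.96 × √(s(1 − s)/n) before clustering and for sensitivity from 85% to 50%, is about 0.10 to 0.14 with 52 cases and 0.14 to 0.20 with 24. With only 1.6 to 3.5 cases per clinic (24/15 to 52/15), a clinic effect on sensitivity may be hard to estimate. Pooled accuracy does not avoid that imprecision; it hides it.
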